**Table 6: Dose Reduction and Modification Guidelines (Continued)**

NCI CTCAE Toxicity Grade	Action	
Other lenalidomide-related non-hematologic AEs	≥ Grade 3	
 
• Interrupt lenalidomide therapy.
 
• May resume lenalidomide when the adverse event resolves to ≤ Grade 2 (decrease one dose level or maintain dose level per the investigator's discretion)
 

A new course of treatment may begin on the scheduled Day 1 of a new cycle if:

- the ANC is  $\geq 500/\mu\text{L}$ ;
- the platelet count is  $\geq 25,000/\mu\text{L}$ ;
- any other lenalidomide-related non-hematologic adverse event that may have occurred has resolved as indicated in [Table 6](#).

If these conditions are not met on Day 1 of a new cycle, the subject will be evaluated weekly and a new cycle will not be initiated until the toxicity has resolved as described above.

Dose interruptions/reductions are permitted for Grade 1 or 2 adverse events at the investigator's discretion.

If a study drug interruption has lasted for 5 weeks, the investigator should contact the medical monitor to discuss whether the subject should be continued on the study.

Site staff are to contact Celgene to record new dose level and obtain new study drug assignment. If the treatment has been withheld and the next treatment cycle is delayed beyond 29 days after Day 1 of the prior treatment cycle, then Day 1 of the next treatment cycle will be defined as the first day that the treatment is resumed. If dose reduction occurs within a cycle, subjects will be given a new 28-day supply bottle, subjects should begin taking study drug at the current cycle day (ie, if reduction occurs on Cycle Day 16, then the subject will take study drug from the new bottle for the remainder of the cycle). Subjects will be required to return empty bottle or any unused drug prior to new drug being dispensed.

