Dose interruptions are also permitted for Grade 1 or 2 adverse events at the investigator's discretion. A guideline for the reduction of the dose of lenalidomide/placebo for DLT is provided (see Section 10.2.1 of the protocol).

Dose re-escalation is permitted if the subject is able to complete 2 full cycles at the reduced dose level without experiencing a DLT or other toxicity deemed to be unacceptable by the investigator or subject and MRD-negative CR has not been achieved yet. If that dose level is again not tolerated, the subject should be de-escalated to the dose below and remain at that tolerated dose level for the rest of the study.

Study visits and serial measurements of safety and efficacy will be performed as outlined in Table 3 of the protocol.

Subjects who discontinue maintenance therapy early (due to reasons other than PD, including unacceptable toxicity) will be followed on study until PD occurs. Subjects will be assessed for response, subsequent CLL therapies, second primary malignancies, AEs, recovery from SAEs and any new SAEs related to study procedures or prior maintenance therapy. Subjects will also be asked to continue to complete the FACT-Leu and EQ-5D questionnaires every 8 weeks.

After Study Discontinuation:

Upon experiencing disease progression, subjects will be followed for survival, information on other CLL treatments, second primary malignancies (reported as SAEs), hospitalizations, and will complete FACT-Leu and EQ-5D questionnaires at each of these visits. Patients who discontinue from progression follow up for reasons other than progression/disease transformation (i.e. withdraw consent from monthly visits, etc) should still be followed for survival, and if possible, date of progression and documentation of progression should be collected on these patients who enter the survival follow up phase prior to progression or disease transformation. Subjects will be followed until all subjects in the study have been followed for at least 5 years from randomization (or died/become lost to follow up before 5 years) or until at least 160 deaths have occurred, whichever comes later.

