6.4.1. Tables

Data in tables will be summarized for each of the treatment groups and overall subjects when appropriate. Tables will contain the number of subjects in the analysis population for each column and the total number. Presentations will be summarized by cycle if applicable. In selected presentations the event or assessment indicating the most severe event by NCI CTCAE toxicity grade or most abnormal assessment (analysis of the “worst” case) for each subject over the course of the study will be summarized.

Time points in the summaries will reflect the time periods described in the protocol and CRF, such as ‘Baseline’, ‘Cycle 1’, ‘Cycle 2’, etc.

Age will be displayed in years and relative days (e.g., study days) will be displayed in days. Dosing exposure and treatment durations will also be displayed in days; all other time intervals will be presented in weeks.

The following descriptive statistics will be displayed for each quantitative variable: n, mean, median, standard deviation (SDev), minimum, and maximum.

Qualitative variables will be presented as category frequencies and percentages. The denominator for calculating percentages will be either the number of subjects in the analysis population or the number of non-missing observations in the treatment group for the particular variable presented. Visit windows will not be used in the data analyses. The cycle number recorded on the CRF, if available, will be used to mark the data collection time points. Actual visit or assessment dates will be used to calculate intervals of time.

If a given table template specifies the summarization of a given qualitative CRF variable and no such response appears on a CRF for any of the subjects in the study population appropriate to that table, the entire row may be deleted from the summary rather than present a row of zeroes for that response.

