9. DRUG EXPOSURE

The following measures of drug exposure will be analyzed for lenalidomide and placebo.

Treatment Duration

The first dose date of lenalidomide or placebo is considered the start date of the overall study treatment. For each cycle, the lenalidomide/placebo start date will be considered the cycle start date and the day before that (after the 1st cycle) will be considered the end day of the previous cycle. The end date of the last cycle will be calculated as the start date of last treatment cycle plus 27 days, unless subject discontinues study or dies before the end of the last cycle, in which case the end date of the last cycle will be the treatment discontinuation date or the death date. The overall study treatment end date will be the same as the end date of the last cycle of the last study drug. The overall treatment duration (days) is defined as:

$$[(\text{The overall study treatment end date}) - (\text{the first study drug start date}) + 1]$$

For each study drug (i.e., lenalidomide or placebo), the treatment duration will also be calculated, and defined as:

$$[(\text{The end of the last cycle of the study drug}) - (\text{the first dose date of the study drug}) + 1]$$

Cumulative Dose

Cumulative dose will be calculated for lenalidomide arm. The cumulative dose is defined as the sum of all doses taken across the treatment period (in milligrams).

Dose Exposure

Dose exposure will be calculated for lenalidomide arm. Dose exposure is defined as the number of days on the study drug during the treatment phase (excluding the periods of dose interruptions).

Average Daily Dose

Average dose will be calculated for lenalidomide arm. Average daily dose is defined as the cumulative dose divided by dose exposure (mg/day).

Dose Intensity

Dose intensity will be calculated for lenalidomide arm. Dose intensity is defined as the cumulative dose divided by treatment duration (mg/day).

Descriptive statistics of treatment duration, cumulative dose, dose exposure, average daily dose, and dose intensity, will be presented by treatment arm. In addition, descriptive statistics for treatment duration in weeks and associated frequency tables, as well as the number of cycles on study drug, will be presented by treatment arm, for both induction therapy period and the whole double-blind treatment period.

The dosing statistics as described above may be presented by cycle.

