11.2.3. Health-Related Quality of Life (HRQL)

For Health-Related Quality of Life (HRQL) by Functional Assessment of Cancer Therapy-Leukemia (FACT-Leu) and EQ-5D, changes from baseline in overall score and sub-scores will be analyzed using repeated measures of ANOVA/ANCOVA using the baseline scores as covariates where appropriate.

Various schemes will be assessed for missing data imputation if needed.

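### The SAP collects HRQL after drug stop and after progression, but gives those scores no time axis shared with on-drug scores

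*SAP*

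**What the plan says.** **Collection.** SAP 5.1 sets two off-drug streams. Subjects who stop maintenance early without progression stay on a fixed questionnaire interval: "Subjects will also be asked to continue to complete the FACT-Leu and EQ-5D questionnaires every 8 weeks". After progression, subjects "will complete FACT-Leu and EQ-5D questionnaires at each of these visits", meaning the follow-up visits, for which the SAP gives no interval. SAP 5.2 lists HRQL as a secondary endpoint.

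**Time points.** SAP 6.4.1 states: "Visit windows will not be used in the data analyses". It continues: "The cycle number recorded on the CRF, if available, will be used to mark the data collection time points". The same section gives cycles as examples of protocol and CRF time periods, and uses actual dates to compute intervals.

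**What a cycle is.** SAP 9: "For each cycle, the lenalidomide/placebo start date will be considered the cycle start date". The last cycle ends 27 days after its start, or earlier on discontinuation or death. Under Protocol 10.2.1 (text after Table 6), if drug has been withheld and the next cycle runs late, "then Day 1 of the next treatment cycle will be defined as the first day that the treatment is resumed".

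**Analysis.** Under SAP 11.2.3, changes from baseline "will be analyzed using repeated measures of ANOVA/ANCOVA using the baseline scores as covariates where appropriate". SAP 13.1 repeats this for subscale scores. Neither section names a time variable, a rule for placing off-drug scores or a cut-off, and both leave the missing-data method open.

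**The concern.** A repeated-measures comparison of arms needs a time index on which both arms' scores can be aligned. The only one the SAP supplies depends on taking study drug. A questionnaire completed after drug has stopped has no natural cycle number, and the usual device for placing it next to on-drug scores, a visit window, is ruled out.

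If the analysis is run by cycle, each time point compares only subjects still on drug. Leaving drug is an outcome, and its causes plausibly differ by arm: the SAP plans for earlier progression on placebo, while stops for toxicity are more likely on the active drug. HRQL in a maintenance trial is meant to weigh delayed progression against toxicity. A comparison conditional on staying on drug has difficulty seeing either, even though SAP 5.1 arranges to collect the scores that would show them.

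On-drug alignment is weakened as well. Every hold that delays the next cycle moves all later cycle numbers away from time since randomization, and moves them further in an arm with more holds.

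**Working it through.** **1. Can an off-drug score be given a time point under the stated rules?**

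- Cycle number: tied to a drug start date (SAP 9), so none arises naturally after the last cycle ends.
- Visit window: excluded (SAP 6.4.1).
- Another protocol or CRF period: allowed in principle, since cycles are only examples. But the 8-weekly visits after early stop, and follow-up visits at an interval the SAP does not give, share no stated schedule with cycles.
- Actual dates: kept and used for intervals, but not named as the HRQL time variable.

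So the scores are collected and dated, but no rule aligns them with on-drug scores.

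**2. How many subjects would this affect?**

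The SAP states no HRQL figure to reproduce. Its planning medians agree with its 61.3% improvement: 20 × 1.613 = 32.26 months for PFS and 3 × 1.613 = 4.839 years for OS.

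Inputs (SAP 6.1): PFS medians 20 and 32.3 months; OS medians 3 and 4.84 years, or 36 and 58.08 months; exponential curves; 160 per arm. No loss to follow-up is assumed.

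For median m, S(t) = 2^(−t/m). PFS events include death, so S_PFS is the share alive without progression and S_OS the share alive. Among the living, the share past progression is 1 − S_PFS/S_OS.

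Month 24:
- Placebo: S_PFS = 2^(−24/20) = 0.435; S_OS = 2^(−24/36) = 0.630; 1 − 0.691 = 31%.
- Lenalidomide: S_PFS = 2^(−24/32.3) = 0.597; S_OS = 2^(−24/58.08) = 0.751; 1 − 0.796 = 20%.

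| Month | Placebo: progression-free / alive | Past PD among living | Lenalidomide: progression-free / alive | Past PD among living |
|---|---|---|---|---|
| 12 | 106 / 127 | 17% | 124 / 139 | 11% |
| 24 | 70 / 101 | 31% | 96 / 120 | 20% |
| 36 | 46 / 80 | 43% | 74 / 104 | 29% |

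Percentages come from unrounded values.

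Over 60 months, mean time in a state is (1 − 2^(−60/m)) × m/ln 2. Placebo: 25.2 progression-free months of 35.6 alive, so 29% of living time follows progression. Lenalidomide: 33.7 of 42.8, so 21%.

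**3. Stops for other reasons (assumed).**

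The documents give no rates, so these are illustrative. Assume non-PD stops at 5% per year on placebo and 20% per year on lenalidomide, independent of progression and death. The share of living subjects on drug at month 24 is then:
- placebo: 0.435 × e^(−0.10) / 0.630 = 63%;
- lenalidomide: 0.597 × e^(−0.40) / 0.751 = 53%.

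With the lenalidomide rate at 5% or 30% per year, its share is 72% or 44%. The size and even the direction of the imbalance depend on that unknown rate.

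**4. Drift within drug (assumed).**

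Two or three holds that each delay the next cycle by 2 to 3 weeks shift later cycle numbers by 2 × 2 = 4 to 3 × 3 = 9 weeks, against an 8-week questionnaire interval. The number and length of holds are assumptions, and the on-drug questionnaire schedule is not visible in the supplied documents.

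**The case against.** The strongest reply is that nothing in the SAP excludes off-drug scores. SAP 6.4.1 sits under reporting conventions for tables. It uses the cycle number only where one exists, treats cycles as examples and keeps actual dates. SAP 6.3.1 puts efficacy analyses on the ITT population unless stated otherwise. SAP 13.1 compares scores at each assessment, with no on-treatment limit. Where the SAP wants later data excluded it says so: SAP 11.2.1 does not count tumor responses after other anti-cancer treatment, and HRQL has no such rule. The CRF is not available, and SAP 5.1 refers to a schedule in protocol Table 3, whereas the supplied protocol's schedule is Table 2 with redacted rows. A follow-up visit label may therefore exist that we cannot see. HRQL is also outside the fixed testing sequence in SAP 11, which names only tumor response and duration of response.

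Much of this stands. A reader might infer that the SAP drops off-drug questionnaires and restricts the comparison to subjects on drug; the documents do not say that, and the ITT wording points the other way. The reply still does not supply the missing rule. The no-window sentence is written for the data analyses, not only for table layout. ITT says who is analysed, not where each score sits in time. Allowing for a missing cycle number does not say what replaces it, and dates used for intervals do not by themselves define the model's time points.

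**Conclusion.** The point holds as an alignment gap, not as a rule that discards data. Under the stated time-point rule, off-drug and post-progression scores cannot be lined up with on-drug scores, and a by-cycle comparison of arms would be conditional on still taking drug.

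Its size, under the SAP's own exponential PFS and OS medians and no loss to follow-up, is about 31% of living placebo subjects and 20% of living lenalidomide subjects past progression at month 24, before any stop for another reason.

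Two larger readings should be avoided. Taking the PFS curve alone puts 1 − 0.435 = 57% and 1 − 0.597 = 40% past progression at month 24, but PFS events include deaths, and the dead complete no questionnaires. Nor can a bias in HRQL points be derived: the documents give no score change after progression or toxicity. An example that assigns a fall only to off-drug subjects will show no on-drug difference by construction.

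The consequence is limited to a secondary endpoint that carries no alpha. The point applies to the SAP as written; the current protocol's visible secondary endpoints are safety and PFS2, with adjacent text redacted.

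**What to change.** For HRQL only, make an exception to the no-window rule in SAP 6.4.1:

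- Index assessments by days since randomization, from recorded dates.
- Use 8-week targets, assign the nearest assessment to each, and state a tie-break rule. Where only follow-up visits exist, use wider targets matched to that visit interval, and state the interval in the SAP.
- State in SAP 11.2.3 and 13.1 that every collected assessment enters the ITT repeated-measures comparison, whether or not the subject is on drug or has progressed.
- Keep the by-cycle display as a supportive on-treatment summary.

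The cost is a short SAP revision and a little programming, with no new data collection. The downside is one of interpretation: scores after progression also reflect later therapies, and the report should say so.

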5.2. Study Endpoints

For all the efficacy endpoints, the determination of responses (including progression of disease) is based on the central adjudication committee (CAC) review of the CLL response data using IWCLL guidelines for the diagnosis and treatment of chronic lymphocytic leukemia [Appendix 22.4 of the protocol]

Co-primary Endpoints

- Progression-Free Survival (calculated as the time from randomization to the first documented progression confirmed by a blinded, independent Response Adjudication Committee or death due to any cause during or after the treatment period, whichever occurs first)
- Overall Survival (calculated as the time from randomization to death from any cause).

Secondary Endpoints

- Safety [type, frequency, and severity of adverse events (AEs) and relationship of AEs to lenalidomide]
- Tumor Response, including evaluation of minimal residual disease (MRD) by flow cytometry (improvement of the quality of response)
- Duration of response
- Health-Related Quality of Life (HRQL) by Functional Assessment of Cancer Therapy-Leukemia (FACT-Leu) and EQ-5D

- Progression Free Survival 2 (PFS2)

5.3. Data and Analysis Quality Assurance

This protocol is conducted under the sponsorship of Celgene Corporation. The data collection and management will be performed according to the Celgene Standard Operating Procedures (SOP). The quality of the analyses will be verified through a programming validation process. At a minimum, all tables of key efficacy and safety variables will be validated based on an independent programming of these results.

6. GENERAL STATISTICAL CONSIDERATIONS

6.1. Sample Size

For OS, a 61.3% improvement in median survival from randomization, from 3 years for placebo to 4.84 years on lenalidomide is considered clinically relevant. For PFS, a 61.3% improvement in median time to progression from randomization, from 20 months for placebo to 32.3 months on lenalidomide is considered clinically relevant. The OS and PFS distributions are assumed to be exponential with a constant failure (hazard) rate. When the total number of events is approximately 160 over both treatment arms, then a two-sided log-rank test with an overall significance level of 0.025 (allowing for the co-primary endpoints) would have 80% power to detect a hazard rate ratio of 0.62. To ensure timely completion of the study, 320 subjects will be enrolled, 160 in each treatment arm.

6.2. Randomization and Stratification

Stratification and randomization will be performed by IVRS, an Interactive Voice Response System, to ensure a 1:1 central randomization. Subjects who are eligible for the study will be randomized (1:1) to receive lenalidomide or placebo. Subjects will be stratified at randomization by: 1) their response to second-line induction therapy (PR, nPR, CRi or CR versus MRD-negative CR); 2) age (≤ 70 versus > 70 years); and 3) presence of at least one of the following poor prognostic factors: 11q deletion, 17p deletion, unmutated IgV_H or $\beta 2M > 4.0$ mg/L (Yes versus No versus Unknown).

6.3. Analysis Populations

6.3.1. Intent-to-Treat (ITT) Population

The Intent-to-Treat (ITT) population is defined as all subjects who are randomized, independent of whether they received study treatment or not. The ITT population will be used for the primary efficacy analysis.

Subject disposition, demographics, baseline characteristics, and all efficacy analyses will be based on the ITT population unless specified otherwise. All subjects in the ITT population will be analyzed according to the treatment they were randomized to receive and not according to what they actually received, if different.

6.3.2. Safety Population

The safety population is defined as all randomized subjects who receive at least 1 dose of the study treatment (either lenalidomide or placebo).

Drug exposure and all safety analyses (including adverse events, labs, and deaths) will be based on the safety population. Subjects will be analyzed according to the initial treatment actually received.

6.4. Reporting Conventions

The algorithms, imputations, and conventions that will generally apply to programmed manipulations of the data for summary tabulations and individual subject data listings are described in this section.

Summary tables, listings, and any supportive SAS output will include a “footer” of explanatory notes that will indicate, at a minimum, the:

- Program source (e.g, SAS program name, including the path, that generates the output) and
- Data extraction date (e.g, the database lock date).

The purpose of the data extraction date is to link the output to a final database, either active or archived, that is write-protected for replication and future reference. An output date will also appear on each output page and will indicate the date the output was generated by the analysis program.

6.4.1. Tables

Data in tables will be summarized for each of the treatment groups and overall subjects when appropriate. Tables will contain the number of subjects in the analysis population for each column and the total number. Presentations will be summarized by cycle if applicable. In selected presentations the event or assessment indicating the most severe event by NCI CTCAE toxicity grade or most abnormal assessment (analysis of the “worst” case) for each subject over the course of the study will be summarized.

Time points in the summaries will reflect the time periods described in the protocol and CRF, such as ‘Baseline’, ‘Cycle 1’, ‘Cycle 2’, etc.

Age will be displayed in years and relative days (e.g., study days) will be displayed in days. Dosing exposure and treatment durations will also be displayed in days; all other time intervals will be presented in weeks.

The following descriptive statistics will be displayed for each quantitative variable: n, mean, median, standard deviation (SDev), minimum, and maximum.

Qualitative variables will be presented as category frequencies and percentages. The denominator for calculating percentages will be either the number of subjects in the analysis population or the number of non-missing observations in the treatment group for the particular variable presented. Visit windows will not be used in the data analyses. The cycle number recorded on the CRF, if available, will be used to mark the data collection time points. Actual visit or assessment dates will be used to calculate intervals of time.

If a given table template specifies the summarization of a given qualitative CRF variable and no such response appears on a CRF for any of the subjects in the study population appropriate to that table, the entire row may be deleted from the summary rather than present a row of zeroes for that response.

